7.1.2 Secondary endpoints and comparisons

1. Percentage of time of glucose levels spent in target range, comparing fast-acting insulin-plus-pramlintide closed-loop delivery vs. regular insulin-plus-pramlintide closed-loop delivery.
2. Percentage of time (8:00-8:00) of glucose levels spent:
 - a.* between 3.9 and 7.8 mmol/L; *b.* between 3.9 and 10 mmol/L; *c.* below 3.9 mmol/L; *d.* below 3.3 mmol/L; *e.* below 2.8 mmol/L; *f.* above 7.8 mmol/L; *g.* above 10 mmol/L; *h.* above 13.9; *i.* above 16.7 mmol/L.
3. Percentage of overnight time (23:00-8:00) of glucose levels:
 - a.* between 3.9 and 7.8 mmol/L; *b.* between 3.9 and 10 mmol/L; *c.* below 3.9 mmol/L; *d.* below 3.3 mmol/L; *e.* below 2.8 mmol/L; *f.* above 7.8 mmol/L; *g.* above 10 mmol/L; *h.* above 13.9; *i.* above 16.7 mmol/L.
4. Standard deviation of glucose levels as a measure of glucose variability.
5. Total insulin delivery.
6. Total pramlintide delivery.
7. Mean glucose level during: *a.* the overall study period; *b.* overnight period.
8. Mean insulin concentration.
9. Mean glucagon concentration.
10. Mean amylin concentration.
11. Number of participants experiencing hypoglycemia requiring oral treatment during: *a.* the overall study period; *b.* the night.
12. Gastrointestinal symptoms during the treatment optimization (i.e., the minimum 10 days prior to the 24-hour closed-loop visits) and during the 24-hour closed-loop visits.

7.2 Sample Size and Power Calculations

The power calculations aim to compare the effects of the interventions on the primary endpoint (time in target range), made at the $\alpha=0.05/2$ significance level: **i)** fast-acting insulin-alone closed-loop delivery and fast-acting insulin-plus-pramlintide closed-loop delivery; **ii)** fast-acting insulin-alone closed-loop delivery and regular insulin-plus-pramlintide closed-loop delivery.

The anticipated difference in time in target range was estimated from Weinzimer et al [6]. In that study, pramlintide increased the time spent in target range by 4%. In our study, we infuse pramlintide during the night too, and we anticipate that will improve glucose control even more. We anticipate that the insulin-plus-pramlintide closed-loop delivery will increase the percentage of time spent in target range by 7% (SD=10%) compared to the insulin alone closed-loop system. The standard deviation of the differences in the percentage of time in target range is estimated from our previous studies. It has always been between 9% and 11% for all comparisons that we usually make (sensor-augmented pump therapy, single-hormone artificial pancreas, and dual-hormone artificial pancreas).

Using the typical sample size formula for paired t-test, we calculated that 22 participants would provide 80% power at the 2.5% (0.05/2) significance level to detect differences between the interventions in the primary comparison. To account for anticipated drop-outs, technical problems, and remaining uncertainty in power calculations, 28 participants will be recruited.

Participants who do not complete one fast-acting insulin-alone closed-loop intervention and at least one insulin plus-pramlintide closed-loop intervention will be replaced in the enrollment process, will not be included in the analysis, and will not count toward the recruitment goal.

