4.1 Trial Design

This study is a randomized, three-way, crossover trial to compare the efficacy of **i)** fast-acting insulin-plus-pramlintide closed-loop delivery, **ii)** regular insulin-plus-pramlintide closed-loop delivery, and **iii)** fast-acting insulin-alone closed-loop delivery in regulating glucose levels over a period of 24 hours in a study on adults in inpatient settings. Insulin (fast-acting and regular) and pramlintide are given with fixed ratio (6 µg of pramlintide for each unit of insulin).

Before each 24-hour intervention visit, the participant's insulin therapy (basal rates and insulin-to-carbohydrate ratios) will be optimized for a minimum of 10 days, with a target of 14 days. If a participant is randomized to either rapid or regular insulin-plus-pramlintide arms, pramlintide will be infused using a second pump at a fixed ratio for a minimum of 10 days, and insulin therapy will be optimized. Regular insulin will replace participant's usual insulin and will be initiated for a minimum of 10 days, and insulin therapy will be optimized.

There will be a wash-out period of 0 to 42 days between the three intervention arms (termination of 24-hr intervention and start of next optimization period).

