5.3 Randomization

Each study participant will be assigned a unique anonymous identification number, which will be used throughout the study. A blocked balanced randomization will be used to determine the order of the interventions.

Participants will be randomized to either **i)** fast-acting insulin-plus-pramlintide closed-loop delivery, **ii)** regular insulin-plus-pramlintide closed-loop delivery, and **iii)** fast-acting insulin-alone closed-loop delivery.

Randomization envelopes will be opened after admissions visit 1.

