5.4 Treatment Optimization

The optimization period will last for a minimum of 10 days, with a target of 14 days. During this optimization period, each participant will wear a glucose sensor. A research team member will contact (by phone or email) study participants in order to optimize their treatment parameters (insulin to carbohydrate ratios, basal rates, etc.). The insulin dose will be titrated to meet target glucose according to the continuous glucose sensor. Research team might ask study participants to present in person if deemed necessarily for treatment optimization. In addition, gastrointestinal symptoms (nausea, vomiting, bloating, and heart burn) will be evaluated during the optimization period, and during the

inpatient interventions. Intervention visits will be conducted after this optimization period. Similar contact and therapy optimization procedure will be applied prior to each intervention.

During days when participant will be wearing the CGM sensor he should be advised to avoid consumption of drugs containing acetaminophen due to possible effect on accuracy of glucose readings. If acetaminophen is part of the subject's standard therapy, the study physician will discuss alternative treatments with the participant.

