8.1.1 Administration

Pramlintide will be administered via a Medtronic pump (Minimed® Veo™ or 630G, Medtronic) at a fixed ratio of pramlintide per unit (U) of insulin. During the study, pramlintide will be infused at:

- 3 µg of pramlintide per unit (U) of insulin in the first 0-4 days of the optimization period
- 6 µg of pramlintide per unit (U) of insulin for the remaining of the optimization period and during the intervention visits.

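### Read literally, the completer rule in 7.2 removes early pramlintide leavers from the gastrointestinal endpoint, which is understated if leavers are more often symptomatic, and it discards usable pairs for secondary endpoint 1

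*Combined protocol and SAP*

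**What the plan says.** All references are to the combined protocol and SAP.

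- **Rule.** The last sentence of 7.2 concerns participants who lack either the insulin-alone visit or any completed pramlintide visit. They "will be replaced in the enrollment process, will not be included in the analysis, and will not count toward the recruitment goal". Neither 7.1, 7.3 nor 7.4 names another analysis set or exempts an endpoint.
- **Timing of randomization.** Section 5.3: "Randomization envelopes will be opened after admissions visit 1". The first optimization period comes later, so these are exclusions after randomization.
- **Exposure before the visit.** In either pramlintide arm, "pramlintide will be infused using a second pump at a fixed ratio for a minimum of 10 days" (4.1). Section 8.1.1 steps the ratio up within that period and applies the higher ratio "of pramlintide per unit (U) of insulin for the remaining of the optimization period and during the intervention visits".
- **Symptoms.** Section 5.4 states that "gastrointestinal symptoms (nausea, vomiting, bloating, and heart burn) will be evaluated during the optimization period". Secondary endpoint 12 in 7.1.2 is worded "Gastrointestinal symptoms during the treatment optimization (i.e., the minimum 10 days prior to the 24-hour closed-loop visits", and it adds the closed-loop visits themselves. Section 8.1.2 lists nausea, vomiting and stomach pain among the side effects of pramlintide.
- **Secondary endpoint 1.** This is time in range, "comparing fast-acting insulin-plus-pramlintide closed-loop delivery vs. regular insulin-plus-pramlintide closed-loop delivery" (7.1.2). It makes no use of the insulin-alone visit.
- **Expected losses.** "To account for anticipated drop-outs, technical problems, and remaining uncertainty in power calculations, 28 participants will be recruited" (7.2).

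**The concern.** Endpoint 12 looks at symptoms over a window that opens when pramlintide starts, at least 10 days before the closed-loop visit. The rule in 7.2 keeps a participant only if a pramlintide visit was later completed. Someone who cannot tolerate the infusion and leaves the study in that window has been exposed, and has symptoms inside the endpoint's window, yet is not in the analysed set. The participant is then replaced by someone who did complete. Inclusion would depend on something that intolerance can cause.

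At stake is how endpoint 12 describes the tolerability of continuous pramlintide infusion. A reader of that result would not see these participants without also going through the adverse event records.

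A second, separate loss follows from the same sentence. A participant who completed both pramlintide visits but not the insulin-alone visit supplies exactly the pair that secondary endpoint 1 needs, and is discarded.

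**Working it through.** **1. The plan's own figure.** Section 7.2 gives a difference of 7 points, SD of differences 10, significance level 0.025 and power 80%. For a paired t-test taken as two-sided, n = 22 gives noncentrality (7/10) × √22 = 3.28 on 21 degrees of freedom and power 80.02%. The stated 22 reproduces. The point below does not touch it.

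**2. Who is excluded.** Let A be insulin-alone, F fast-acting insulin plus pramlintide, and R regular insulin plus pramlintide. The rule keeps a participant only if A and at least one of F or R were completed. Suppose a participant leaves for good during a pramlintide optimization period. Section 5.3 does not list the sequences, so all six orders are assumed.

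| Order | Completed before exit in first pramlintide period | Result | Completed before exit in second pramlintide period | Result |
|---|---|---|---|---|
| A F R | A | excluded | A, F | kept |
| A R F | A | excluded | A, R | kept |
| F A R | none | excluded | F, A | kept |
| R A F | none | excluded | R, A | kept |
| F R A | none | excluded | F | excluded |
| R F A | none | excluded | R | excluded |

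First pramlintide period: excluded in 6 of 6 orders. Second: excluded in 2 of 6, those with insulin-alone last. With only the three orders of a Latin square, the counts are 3 of 3 and 1 of 3, so the conclusion is the same.

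A participant who stops one pramlintide arm but stays and completes the other pramlintide visit and A is kept. The mechanism needs a permanent exit.

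**3. Pairs lost for secondary endpoint 1.** In F R A and R F A, a participant who leaves in the third period has completed F and R but not A. The rule excludes this participant although the F–R pair is complete.

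**4. Condition for understatement.** Take one pramlintide arm with s of 28 analysed participants symptomatic. Restore q excluded participants who started that arm, k of them symptomatic. The share becomes (s + k)/(28 + q). This exceeds s/28 if and only if k/q > s/28.

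**5. Illustration.** The documents give no symptom rate or dropout rate. Assume s = 6, so 6/28 = 21.4%.

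| Restored to the arm (q) | All symptomatic (k = q) | None symptomatic (k = 0) |
|---|---|---|
| 1 | 7/29 = 24.1% | 6/29 = 20.7% |
| 2 | 8/30 = 26.7% | 6/30 = 20.0% |
| 3 | 9/31 = 29.0% | 6/31 = 19.4% |

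The change runs from +2.7 to +7.6 points if all restored participants are symptomatic, and from −0.7 to −2.1 points if none are. The calculation is per arm because someone who leaves in the first pramlintide period has started only one pramlintide arm.

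**The case against.** The strongest objection is scope. The sentence closes 7.2, which opens by stating that it concerns the primary endpoint, and its condition is exactly the pair needed for a primary comparison. The analysis it mentions may therefore be the primary analysis only. Section 7.4 gives no method or population for endpoint 12, so one may say that its population is simply unstated. This stands in part: the exclusion from endpoint 12 is the literal reading and not a certainty. It does not remove the point, because the sentence is unrestricted, nothing elsewhere limits it, and an analyst following the text would apply it throughout.

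Second, 10.1 collects adverse events from consent onward, including discontinuation of therapy as an outcome, so these cases are not lost to the trial. That stands and softens the consequence. It does not put the leavers into endpoint 12, and the plan does not say how adverse events will be summarized or in whom.

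Third, direction is not shown. That stands too. Exits for technical reasons, or failed insulin-alone visits, could leave the symptom share unchanged or even overstated, as the last column of the illustration shows.

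Fourth, 5.4 gives no schedule or instrument for the symptom evaluation, so how complete the data on leavers would be is not known.

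A reader might also infer the size of the loss from the difference 28 − 22 = 6. The documents do not support that: replaced participants do not count toward the recruitment goal, so they come on top of the 28. Nor do counts of treatment orders give a probability of exclusion, since nothing says how likely an exit is in each period.

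**Conclusion.** The point holds in a conditional form. As written, 7.2 removes from every endpoint anyone who leaves for good in the first pramlintide optimization period (6 of 6 orders), and in the second when insulin-alone comes last (2 of 6). Endpoint 12 is understated if those removed are more often symptomatic than those kept. The side effects listed in 8.1.2 make this plausible, but neither its direction nor its size can be determined from the documents. The per-arm rise from 21.4% to between 24.1% and 29.0% is an illustration that rests on an assumed 6 of 28 and on 1 to 3 restored participants, all symptomatic. The loss of complete pairs for secondary endpoint 1 follows directly from the wording and needs no assumption about symptoms, though its number is also unknown.

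Two stronger readings should be resisted. A reader might infer that the primary time-in-range comparisons are biased; the documents give no basis for a direction or size there, and a completer rule for those comparisons can stay. A reader might also say that the rule cannot be applied because a visit stopped under 6.4.2 or 6.4.3 is not classed as completed or not. That is a missing detail and does not make the rule unworkable.

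Overall this is a cheap improvement of minor to moderate severity.

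**What to change.** - In 7.2, keep the replacement of participants and the completer rule, but state that the exclusion applies to the two primary comparisons only.
- In 7.1.2 or 7.4, state that endpoint 12 is analysed by arm in everyone who started the relevant optimization period or visit, replaced participants included, using symptoms recorded up to the time of leaving.
- Report discontinuations and replacements by arm, period and reason.
- Include every participant with both pramlintide visits in secondary endpoint 1, whether or not the insulin-alone visit was completed.

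The cost is slightly more reporting. No new data collection is called for: 5.4 already provides for symptom evaluation and 10.1 for recording discontinuation as an outcome of an adverse event. The sample size and the primary analysis do not change. The one downside for the sponsor is that the tolerability figure may come out less favourable.

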7.3 Level of Significance

5% significance threshold will be used to declare statistical significance. Bonferroni correction will be used for the two primary comparisons. No formal correction will be applied for the secondary comparisons.

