Co-administration of pramlintide at mealtimes along with rapid-acting insulin may lead to an immediate post-prandial plasma sugar reduction followed by a delayed hyperglycemia [8]. The decrease in blood sugar levels in the early postprandial period are due to the faster action time of pramlintide combined with the fast action of rapid-acting insulin. Literature data suggests that the pharmacodynamics of regular insulin may better match the effect of pramlintide compared to the pharmacodynamics of fast-acting insulin (Figure 1). Moreover, the cost of regular insulin is significantly lower than fast-acting insulin. Therefore, if a similar (or better) glucose profile can be achieved with regular insulin-plus-pramlintide compared to fast-acting insulin-plus-pramlintide, then a co-formulation employing regular insulin should be prioritized.

[figure not shown]

Figure 1 Postprandial glucose profiles in type 1 diabetes following injections of regular insulin (left) or insulin lispro (right) plus either placebo or 60 μ g pramlintide bolus at meal (breakfast) time. Reprinted from the Symlin label [9].

Therefore, in this protocol, we aim to assess the effect of the simultaneous, closed-loop, basal-bolus infusion of pramlintide with insulin at a fixed ratio in controlling glucose levels. In the first experimental arm, we propose to infuse pramlintide with fast-acting insulin. In the second experimental arm, pramlintide will be infused with regular insulin. The control arm will be fast-acting insulin-alone closed-loop system.

2 Trial Objectives

The aim of the study is to assess the efficacy of the simultaneous, closed-loop, basal-bolus infusion of pramlintide with fast-acting insulin at a fixed ratio and pramlintide with regular insulin at a fixed ratio in controlling glucose levels compared to fast-acting insulin-alone closed-loop infusion. Pramlintide will be initiated for a minimum of 10 days with a target of 14 days before the closed-loop experiment,

which will mimic more closely the performance of the system during the chronic use of pramlintide rather than its acute use. Regular insulin will replace participant's usual insulin and will be initiated for a minimum of 10 days with a target of 14 days before the closed-loop experiment.

3 Hypothesis

Primary hypotheses:

1. During closed-loop control, the simultaneous basal-bolus infusion of pramlintide and fast-acting insulin improves glucose control compared to fast-acting insulin-alone infusion.

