2. During closed-loop control, the simultaneous basal-bolus infusion of pramlintide and regular insulin improves glucose control compared to fast-acting insulin-alone infusion.

4 Study Design

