7.1 Study Endpoints

7.1.1 Primary comparisons

Percentage of time of glucose levels spent in target range (defined to be between 3.9 and 10.0 mmol/L). The following comparisons will be done:

- i) Fast-acting insulin-plus-pramlintide closed-loop delivery vs. fast-acting insulin-alone closed-loop delivery;
- ii) Regular insulin-plus-pramlintide closed-loop delivery vs. fast-acting insulin-alone closed-loop delivery.

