7.4 Statistical Tests

The effect of the treatments on the continuous endpoints will be estimated using a linear mixed effect model. The hypothesis of no sequence effect will always be tested to check for carry-over effects. The model will be suited for repeated observations, i.e., adjusts for patient-level intracorrelation. Residual values from the regression model will be examined for an approximate normal distribution. If values are highly skewed, a transformation or nonparametric analyses will be used. Number of participants

requiring treatment for hypoglycemia will be compared between the two interventions using McNamer test.

8 Investigational Products

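### Cheap improvement, not an error: Holm instead of single-step Bonferroni lifts power per primary comparison from 80% to 84–86% at n = 22 if both arms work as assumed, within the same 5% family-wise bound

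*Combined protocol and SAP*

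**What the plan says.** Section 3 states two separate primary hypotheses, one for each pramlintide arm. The first is that, during closed-loop control, "the simultaneous basal-bolus infusion of pramlintide and fast-acting insulin improves glucose control compared to fast-acting insulin-alone infusion". The second is that "the simultaneous basal-bolus infusion of pramlintide and regular insulin improves glucose control compared to fast-acting insulin-alone infusion". Section 7.1.1 matches them with two primary comparisons on time in target range, both against the fast-acting insulin-alone arm.

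Section 7.3 sets an overall 5% threshold and adds that "Bonferroni correction will be used for the two primary comparisons". No step-down or gatekeeping procedure appears anywhere in the document.

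Section 7.2 sizes each comparison on the same footing: "22 participants would provide 80% power at the 2.5% (0.05/2) significance level". It assumes a difference of 7 percentage points with an SD of 10, without distinguishing the two pramlintide arms, and plans to recruit 28. On the SD it says: "It has always been between 9% and 11% for all comparisons that we usually make". The 7 points are an extrapolation from an earlier closed-loop study in which "pramlintide increased the time spent in target range by 4" percent.

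For the analysis itself, Section 7.4 says: "The effect of the treatments on the continuous endpoints will be estimated using a linear mixed effect model".

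**The concern.** Single-step Bonferroni tests both hypotheses at 2.5% whatever happens. Once one of the two has been rejected, only one hypothesis remains that could be falsely rejected, and it can be tested at the full 5% without breaking the family-wise bound. Holding it at 2.5% gives up power for no improvement in the guarantee.

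The loss falls in the scenario for which the trial is planned, since Section 7.2 assumes the same benefit for both arms. It also falls on a weaker second arm, which is a realistic possibility given that the assumed 7 points exceed the earlier 4. What is at stake is the chance of confirming a true second hypothesis. The plan does not require both to succeed, so power per comparison is the main measure and power for both is a secondary one.

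**Working it through.** **Inputs from the document.** Section 7.2: difference 7, SD of the paired differences 10 (range 9 to 11), n = 22, 28 recruited, paired t-test, 0.05/2 per comparison. Section 7.3: 5% overall, Bonferroni.

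**Assumptions.** The tests are two-sided; the document does not say so, but only this reading gives 22 exactly. The correlation ρ between the two paired differences is not given, so 0, 0.5 and 0.8 were used. The middle value follows from equal arm variances σ² and equal within-person correlations r. With a shared control arm C, Cov(A−C, B−C) = σ²(1−r) and Var(A−C) = 2σ²(1−r), so ρ = 0.5.

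**Step 1: the plan's own figure.** Noncentrality = (7/10)·√22 = 3.283 on 21 degrees of freedom; two-sided 2.5% critical value 2.414. Exact noncentral t power is 0.8002. The stated 22 participants and 80% reproduce. At an unadjusted 5% (critical value 2.080) power is 0.879, which is the ceiling for any procedure that tests each comparison at no more than 5%.

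**Step 2: Holm by hand at ρ = 0.** A comparison is won if its p-value is below 0.025, or if it lies between 0.025 and 0.05 and the other is below 0.025.

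- Power per comparison: 0.800 + 0.800 × (0.879 − 0.800) = 0.863.
- Power for both: 0.879² − (0.879 − 0.800)² = 0.766, against 0.800² = 0.640 with Bonferroni.

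**Step 3: other correlations.** Simulated paired t-tests, both methods applied to the same data (4,000,000 trials per scenario). Where two values are joined by an arrow, the first is Bonferroni and the second Holm.

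| Scenario (SD 10 unless stated) | Measure | ρ = 0 | ρ = 0.5 | ρ = 0.8 |
|---|---|---|---|---|
| Effects 7/7, n = 22 | per comparison | 0.800 → 0.863 | 0.800 → 0.853 | 0.800 → 0.843 |
| Effects 7/7, n = 22 | both | 0.641 → 0.766 | 0.684 → 0.789 | 0.726 → 0.811 |
| Effects 7/7, n = 22 | at least one (same for both) | 0.960 | 0.916 | 0.874 |
| Effects 7/7, n = 22, SD 9 | per comparison | 0.882 → 0.929 | 0.882 → 0.921 | 0.882 → 0.913 |
| Effects 7/7, n = 22, SD 11 | per comparison | 0.713 → 0.784 | 0.713 → 0.773 | 0.713 → 0.763 |
| Effects 7/7, n = 28 | per comparison | 0.901 → 0.942 | 0.901 → 0.935 | 0.901 → 0.928 |
| Effects 7/7, n = 28 | both | 0.811 → 0.893 | 0.833 → 0.901 | 0.856 → 0.911 |
| Effects 7/4, n = 22 | weaker arm | 0.317 → 0.409 | 0.317 → 0.418 | 0.317 → 0.428 |
| Effects 4/4, n = 22 | per comparison | 0.317 → 0.353 | 0.317 → 0.359 | 0.317 → 0.359 |
| Effects 7/0, n = 22 | effective arm | 0.800 → 0.802 | 0.800 → 0.802 | 0.800 → 0.801 |
| Effects 7/0, n = 22 | ineffective arm declared | 0.025 → 0.045 | 0.025 → 0.043 | 0.025 → 0.040 |
| Effects 0/0, n = 22 | any rejection (same for both) | 0.049 | 0.047 | 0.041 |

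Two checks. The expected number of rejections equals P(at least one) + P(both), so at ρ = 0.5 Holm's power per comparison must be (0.916 + 0.789)/2 = 0.853, as found. With effects 7/0 and ρ = 0, the false declaration rate is 0.025 + 0.025 × 0.800 = 0.045, as found.

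The n = 28 rows assume that all 28 complete all three arms. Section 7.2 also counts participants with only one pramlintide arm, so these rows are an upper limit on power.

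**Step 4: a model closer to Section 7.4.** A mixed model with equal variances and correlations, ρ = 0.5, 42 pooled degrees of freedom and n = 22 (2,000,000 trials) gives 0.827 → 0.871 per comparison and 0.728 → 0.816 for both with effects 7/7. With effects 7/0 the ineffective arm is declared in 0.025 → 0.044.

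**The case against.** The strongest reply is that this is a preference. Bonferroni is prespecified, matches the sizing, biases no estimate and gives simple intervals that agree with its decisions. That is correct, and it is why the point is offered as an improvement only.

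Several limits on the benefit also stand:

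- The gain of 4 to 6 points per comparison belongs to the calculated minimum of 22 and needs both arms to work. With 28 complete participants it is about 3 to 4 points, and with effects of 4/4 at n = 22 it is also about 4 points, from a base of 32%.
- The chance of winning at least one comparison does not change. The secondary contrast between the two pramlintide arms is not helped.
- The 86% end of the range needs ρ = 0, although the two differences share a control arm. At ρ = 0.5 the figure is 85%. Above 0.8 the gain shrinks further (83.7% at 0.9) and vanishes at 1.
- If one arm works and the other does not, false declaration of the ineffective arm nearly doubles, though it stays below the 5% that the plan accepts.
- Any additional Holm rejection has a p-value between 0.025 and 0.05, so its 97.5% interval includes zero. From the power-for-both figures with effects 7/7 at n = 22, this happens in 8.5% (0.811 − 0.726) to 12.5% (0.766 − 0.641) of trials. The report has to explain it.

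None of this defeats the proposal. Holm cannot lose a rejection that Bonferroni would make, and its error bound does not depend on the correlation or on the test used, provided each p-value is valid.

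**Conclusion.** The point holds as a cheap improvement. Section 7.3 is valid as written and Section 7.2 reproduces. Under the plan's assumptions at n = 22, Holm raises power per comparison from 80% to 84–86% and the chance of confirming both hypotheses from 64–73% to 77–81%. Over the stated SD range the change per comparison is 88% to 91–93% (SD 9) and 71% to 76–78% (SD 11). A weaker second arm with a true difference of 4 gains most, from 32% to 41–43%.

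These figures rest on two-sided tests, an assumed ρ between 0 and 0.8, and both arms being effective. The family-wise bound of 5% needs none of these assumptions.

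**What to change.** In Section 7.3, replace the Bonferroni sentence with a Holm rule for the two primary comparisons: the smaller p-value is tested at 2.5%; if it is significant, the other is tested at 5%; otherwise neither is declared. Report 97.5% intervals for both differences, with a note that they correspond to Bonferroni decisions and may include zero for a comparison that Holm declares significant. Leave the sample size in Section 7.2 as calculated; its 80% at 2.5% then becomes a lower bound on the power per comparison.

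The cost is two or three sentences and no added participants, plus notification of the ethics committee as Section 9.5 requires for amendments. The change has to be made before outcome data are examined; the documents do not show whether the trial had started. The statistical price is the higher chance of declaring an ineffective arm when only the other works (4.0–4.5% at n = 22 and 4.3–4.8% at n = 28, against 2.5%) and intervals that do not match the decisions exactly.
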